### 3 OBJECTIVES AND ENDPOINTS

OBJECTIVES	ENDPOINTS
PRIMARY	
Determine implementation outcomes including acceptability, appropriateness, feasibility, and fidelity.	Acceptability, appropriateness, and feasibility will be quantitatively and qualitatively assessed using 4-item, pragmatic scales and individual stakeholder interviews.  Fidelity of intervention delivery, will be monitored using an adapted version of the Parent Early Start Denver Model (P-ESDM) Caregiver Fidelity Rating System.
SECONDARY	
Determine proximal changes in child and caregiver interactions and caregiver sense of competence	A key proximal outcome will be change from baseline (pre-intervention) to 9-weeks (immediately post-intervention) in caregiver sense of competence measured by the Parent Sense of Competence Scale and child behaviors measured by the sum of 4 items from the JERI (Joint Engagement, Attention to Caregiver, Responsiveness to Partner’s Communication Bids, Fluency and Connectedness).
Other Exploratory behavioral outcomes at 9 weeks and 16 weeks	
Assess core ASD social	• Social Responsiveness Scale-2 (SRS-2)(66-68)

OBJECTIVES	ENDPOINTS
functions, ADHD symptoms, symptoms and adaptive functioning	
 
• Aberrant Behavior Checklist-2 (ABC)(69, 70)
 
• ADHD-RS
 
• VABS-3
 

Assess other aspects of attention and executive function	
 
• Behavioral Rating Inventory of Executive Function (BRIEF)(77, 78)
 

Other Relevant Behaviors	
 
• Child Behavior Checklist (CBCL)(79)
 

Caregiver functioning & attitudes toward treatment	
 
• Caregiver Strain Questionnaire (CSQ)(83, 84)
 

Safety assessments	
 
• Treatment emergent adverse effects assessed based on spontaneous report from parent/caregiver
 

## 4 STUDY DESIGN

### 4.1 Overall Design

The overall study design and key outcomes and assessments are shown in the Schema in the synopsis.

The provided behavioral treatment will be eight consecutive weekly ~60-minute coaching sessions delivered remotely. The ESDM-informed caregiver coaching is a modification of the evidence-based behavioral treatment of ESDM, which is typically delivered as 20 hours/week of 1:1 interaction between the child and a trained therapist over a 2-year period. The ESDM-informed caregiver coaching modification reduces rigid time demands on families and is more likely to be sustainable and available in the current healthcare environment. Additionally, the remote implementation of the intervention allows this to be utilized in pandemic conditions and in rural communities where it may be difficult to travel to an academic center for sessions.

### 4.2 Scientific Rationale for Study Design

The intention of the study is *not* to evaluate the efficacy of the behavioral intervention, which is informed by a widely accepted, clinical intervention that has demonstrated efficacy compared to usual care treatment that did not include ESDM at the time. Instead, we are assessing the feasibility of an adapted caregiver delivered ESDM behavioral intervention given remotely in children with a dual diagnosis of ASD and ADHD.

Our hypothesis, shown below, is that children with ASD+ADHD have poorer outcomes than those with ASD alone because their ADHD symptoms interfere with their engagement in ASD behavioral interventions.

By understanding rates of enrollment, acceptability, appropriateness, and feasibility of a behavioral intervention delivered remotely to caregivers of children with both ASD and ADHD we can begin to develop a more informed **patient centered** phase 2 study which would address both a medication component and behavioral intervention for the treatment of ASD and ADHD.

#### 4.3 Justification for Dose

No study-provided medication

#### 4.4 End of Study Definition

A participant is considered to have completed the study if he or she has completed the endpoint assessments of all phases of the study or has been withdrawn from both treatment and assessments in the study. If a participant chooses to stop behavioral treatment in the study before endpoint assessments, he or she will be requested to complete them on schedule if at all possible. The follow-up visit at 16 weeks following baseline is optional.

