**Description of Sites**

**Enrolling Participants:** Single academic center site in US.

**Description of Study Intervention:** All participants will receive eight consecutive weekly ~60-minute ESDM-informed caregiver coaching sessions.

**Participant Duration:** Total participation is expected to require a maximum of 20 weeks, including optional remote follow-up at 16 weeks. The A+ Treatment diagnostic and screening visits will generally occur between 1 and 6 weeks prior to baseline. ESDM-informed parent coaching will be delivered per the Schedule of Activities (SOA) for 8 weeks. Endpoint assessments will be completed after the final coaching visit. No medication will be provided by the study team. The final assessment will be obtained at 16 weeks after baseline.

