1.2 Schema

**Figure 1: A+ Treatment Schema** A+ Treatment staff will meet with parents/caregivers to explain the study and to review the informed consent document with them. Eligibility in the A+ Treatment study will include meeting diagnostic and age criteria. ESDM-informed caregiver coaching begins after baseline assessments and will continue for 8 weeks. The primary outcome assessments will evaluate feasibility of ESDM-informed caregiver coaching in children ages 3-10. This study will be conducted remotely.

Week -2 to -1	Week 0	Weeks 1-8	Week 9	Week 16
Screen & Confirm Diagnose	Baseline	ESDM Sessions	Endpoint	Remote Follow-up
Diagnostic assessments Cognitive testing Parent questionnaires Vineland-3 parent report	Joint engagement Social communication ADHD symptoms AIM Parent questionnaires	ESDM Caregiver Fidelity ESDM Caregiver Self-Monitoring ESDM Coaching Fidelity	Joint engagement Social communication ADHD symptoms AIM Qualitative interview Vineland-3 parent report Parent questionnaires	Social communication ADHD symptoms Parent Questionnaires Vineland-3 parent report

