### 1.3 Schedule Of Activities (SoA)

ACTIVITIES	Consent & Diagnostic Confirmation a & Feedback	Baseline/and call with Coach	Coaching W1	Coaching W2	Coaching W3	Coaching W4	Coaching W5	Coaching W6	Coaching W7	Coaching W8	Endpoint Assessments	Remote Follow-up
Typical Week offset from baseline A	prior	0	1	2	3	4	5	6	7	8	9	16
Informed consent	X											
Demographics, ACE subject Med Hx, ACE Fam Hx, Intervention Hx,  Spence	X											
Diagnostic & Cognitive testing	X											
ESDM-informed caregiver coaching		Brief call	X	X	X	X	X	X	X	X		
P-ESDM Caregiver Self-Monitoring checklist**			X	X	X	X	X	X	X	X		
ESDM coach fidelity *			*	*	*	*	*	*	*	*		
ESDM caregiver fidelity		X	X	X	X	X	X	X	X	X	X	
Remote PCIT												
JERI coding of child/ caregiver items		X									X	
Qualitative Interview											X	
AIM, IAM, FIM											X	
Caregiver Sense of Competence Scale		X									X	X
App S2K		X									X	X
ABC		X					X				X	X
Vineland-3 parent questionnaire	X										X	X
CBCL	X										X	X
ADHD-RS-parent	X										X	X
SRS-2	X	(X) +									X	X
Caregiver Strain Questionnaire		X									X	X
Condensed (non-ASD) Med Hx  , AE's, Con Meds,		X	X	X	X	X	X	X	X	X	X	
BRIEF	X	(X) +									X	

A: no strict window for visits, but ideally post-baseline visits should be done within ± 7 days (relative to visit each time point from baseline); \*: done once randomly

during sessions 2-8; \*\*: completed by caregiver and coach; **Green text: measures acquired in ARC and in P3**; (X)+: only needs to be done if baseline done more than 3 months prior; 2: non ASD med history only done at baseline visit & diagnostic confirmation is informed by ARC assessments. Participants typically begin study participation within 1-3 months of completing the ARC evaluation (if the participant is eligible). However, we also expect that in some situations, (e.g., due to the COVID-19 pandemic) there may be a delay between the ARC evaluation and participation in the A+ Treatment/Feasibility sub-study. If this happens, the following assessments and/or parent-report forms may be repeated:

- If > 2 years since ARC completion: ASD diagnostic assessment (e.g., BOSA, ADOS, TELE-ASD-PEDS) and cognitive assessment (e.g., WPPSI/WISC, DAYC-2, DAS-2, Mullen)
- If > 6 months since ARC completion: CBCL
- If > 3 months since ARC completion of: SRS-2, VABS, ADHD-RS parent form

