### 9.3.3 Analysis of the secondary endpoints

Proximal child and caregiver outcomes. A key proximal outcome will be change from baseline (pre-intervention) to 9-weeks (immediately post-intervention) in caregiver ) sense of competence measured by the Parent Sense of Competence Scale and child behaviors measured by the sum of 4 items from the JERI (Joint Engagement, Attention to Caregiver, Responsiveness to Partner’s Communication Bids, Fluency and Connectedness) coded by a trained, reliable coder who is naïve with respect to whether the observation is from baseline our outcome using video-recorded caregiver-child interactions.

Aim 2 data analysis: Quantitative measures, including participant demographics, will be summarized using descriptive statistics. Means and standard deviations will be reported for continuous measures, and frequency and percentages are reported for categorical variables. Tabular and graphical summaries of each outcome measure at each assessment point will be generated to assess the degree to which the average in the cohort changes over time (e.g. boxplots of VABS-3 Communication at baseline and follow up). Inference on pre-post change will be based on paired t-tests or, if the assumptions are found to be untenable, the Wilcoxon signed rank test.

---

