### 9.3.8 Exploratory analyses

Additional Exploratory proximal and distal outcomes of interest include: a) caregiver ADHD-RS ratings of the child’s attention. b) Aberrant Behavior Checklist (ABC), including inattention/hyperactivity, social withdrawal, stereotypies, irritability, and inappropriate speech; c) Social Reciprocity Scale-2 (SRS-2) ratings of child’s social communication behavior; d) Caregiver Strain Questionnaire (CSQ) ratings of the impact of the child’s condition on the family and caregiver and quality-of-life; e) Behavior Rating Inventory of Executive Functions (BRIEF) ratings of child’s executive function; and f) Child Behavior

Checklist (CBCL) ratings of child behavioral and emotional problems. Our analysis will focus on graphical displays, which will be complemented by appropriate inferential statistical procedures. For the graphical displays, we will visualize the distribution of proximal and distal outcome measures in histograms to better understand the shape and spread of the distribution of each. In terms of inference, between group change at proximal and distal time points will be based on between group t-tests or, if the assumptions are found to be untenable, the Mann-Whitney U test. Whilst statistical inference is valuable, we anticipate that we will elicit most information through careful data visualization. Change from baseline (pre-intervention) to 16-weeks (8-weeks post-intervention) will be assessed for the VABS-3 Socialization and Communication Subscale Standard Scores.

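### The VABS-3 change contrast that the plan spells out ends at the optional week-16 visit, although Vineland-3 is also scheduled at week 9 and the objectives table lists both time points

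*Combined protocol and SAP*

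**What the plan says.** Section 9.3.8 states: "Change from baseline (pre-intervention) to 16-weeks (8-weeks post-intervention) will be assessed for the VABS-3 Socialization and Communication Subscale Standard Scores". The synopsis (Other Exploratory Endpoints) and Aim 2 in Section 2.3 repeat this. In those two places the other caregiver-rated exploratory measures (ADHD-RS, ABC, SRS-2, CSQ, BRIEF, CBCL) are given a baseline-to-week-9 change, so VABS-3 is set apart.

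Section 4.4 says "The follow-up visit at 16 weeks following baseline is optional", and the synopsis entry on participant duration agrees ("including optional remote follow-up at 16 weeks"). For the week-9 endpoint, Section 4.4 asks families who stop coaching early to complete the assessments on schedule where possible.

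Vineland-3 is collected three times. The Schedule of Activities row "Vineland-3 parent questionnaire" is marked before baseline, at the endpoint and at remote follow-up. The week-9 column of the schema reads "Joint engagement Social communication ADHD symptoms AIM Qualitative interview Vineland-3 parent report Parent questionnaires".

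The objectives table in Section 3 lists VABS-3 under "Other Exploratory behavioral outcomes at 9 weeks and 16 weeks". On method, Section 9.3.3 says "Tabular and graphical summaries of each outcome measure at each assessment point will be generated", with VABS-3 Communication as its example, and then "Inference on pre-post change will be based on paired t-tests or, if the assumptions are found to be untenable, the Wilcoxon signed rank test".

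**The concern.** The plan is not consistent about which change is the VABS-3 endpoint. Three places give one contrast, ending at week 16. The objectives table gives two time points. Section 9.3.3 does not say which visit counts as the post measurement for VABS-3.

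The contrast that is spelled out depends on a visit that families may decline. A paired test uses only children with both scores, so a child with baseline and week-9 scores but no week-16 score adds nothing to it. The supplied text gives no method for missing week-16 scores, no expected attendance, and no comparison of attenders with non-attenders.

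The study is meant to supply pilot data for later combination trials. An adaptive-behaviour change estimated from an unknown fraction of the children, possibly not a typical fraction, would be a weak planning input, and readers could not tell how weak.

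**Working it through.** The plan has no figure to reproduce. Section 9.1 bases the sample size on expected recruitment, with no power, effect size or SD. What follows is illustration.

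**Inputs from the documents.** Planned N is 35 (Section 5), or 30-35 (synopsis and Section 5.5). Attrition is about 15% (Section 5.5), not split by visit.

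**Assumptions, not in the documents.** All attrition falls by week 9. A fraction *a* of week-9 completers attends week 16, taken as 60-90% and also shown at 100%. The SD of change is the same at weeks 9 and 16. Non-attenders' mean change differs from attenders' by 0.5 SD.

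**Formulas.**
- Week-9 children: N × (1 − 0.15), so 35 × 0.85 = 29.75 and 30 × 0.85 = 25.5.
- Week-16 pairs: that number × *a*, rounded down.
- Standard error relative to week 9: 1/√*a*.
- 95% CI half-width for the mean change, in SDs of change: t(0.975, n − 1)/√n.
- Bias of the attender mean against the mean of all week-9 completers. The full mean is *a* × (attender mean) + (1 − *a*) × (non-attender mean), so the bias is (1 − *a*) × (attender mean − non-attender mean). Its absolute size here is (1 − *a*) × 0.5 SD.

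**Results.**

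| Attendance *a* | SE ratio | Bias (SD) | Pairs, N = 35 | Half-width (SD) | Pairs, N = 30 | Half-width (SD) |
|---|---|---|---|---|---|---|
| 100% | 1.00 | 0 | 29 | 0.38 | 25 | 0.41 |
| 90% | 1.05 | 0.05 | 26 | 0.40 | 22 | 0.44 |
| 80% | 1.12 | 0.10 | 23 | 0.43 | 20 | 0.47 |
| 60% | 1.29 | 0.20 | 17 | 0.51 | 15 | 0.55 |

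The half-widths grow slightly more than the SE ratio because counts are rounded down and the t quantile rises as n falls.

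The sign of the bias is open. If the more satisfied families return, the mean change is too favourable. If families with continuing difficulties return, it is too unfavourable.

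**The case against.** The strongest reply is that the plan does not ignore week 9. The objectives table names it for VABS-3. Section 9.3.3 promises tables as well as plots for every measure at every assessment point, and its paired inference can be read as covering week-9 change. This stands. A reader might infer that VABS-3 is analysed only at week 16, and the documents do not support that. What is missing is a clear statement of which changes will be estimated, and of what happens when week 16 is skipped.

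A reader might also infer that the result rests on self-selected, more engaged families and is biased upward. The documents do not show this either. They give no attendance rate for either visit and no evidence on direction. Several features favour attendance: week 16 is remote and paid (Section 5.5), rating scales can be done online, by phone or on paper (Section 10.1.5), and Section 9.3.1 promises efforts to collect all outcomes on all participants. The change log mentions missed week-16 physician visits, but that procedure has been removed and says nothing about Vineland-3 completion.

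Nor should week 9 replace week 16. Week 16 asks a distal question, 8 weeks after coaching ends, and is a legitimate choice of time point.

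Two further points stand. A repeated-measures model in about 30 children relies on missingness being explained by the observed scores, so it would not remove selection on unmeasured engagement. And Section 9.3.1 foresees a final statistical analysis plan before database lock, so the gap in missing-data handling is a gap in the text supplied.

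None of this resolves the conflicting time points, or the loss of children from the named contrast under a paired test.

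**Conclusion.** The point holds as a minor one. The VABS-3 change that the plan defines in three places ends at an optional visit, the objectives table gives two time points, and the stated paired test drops any child without a week-16 score even though a week-9 score is scheduled.

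The size is unknown. Under the stated assumptions, 60-90% attendance gives a standard error 5-29% larger than at week 9 and a bias of 0.05-0.20 SD in either direction. At full attendance there is no loss and no bias. These figures depend on assumed attendance, equal change SDs at the two visits and an assumed 0.5 SD difference, none of which the documents supply.

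The stakes are limited. VABS-3 is exploratory, Section 4.2 says that the study is not meant to evaluate efficacy, and no feasibility conclusion depends on this contrast.

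**What to change.** 1. Reconcile the synopsis, Aim 2 and Section 9.3.8 with the Section 3 objectives table by naming both VABS-3 changes, baseline to week 9 and baseline to week 16, with week 16 kept as the distal contrast.
2. Estimate both changes from one repeated-measures model, with visit as a categorical effect, using all available baseline, week-9 and week-16 scores. Children who miss week 16 then still contribute. State the missing-data assumption.
3. Report the number of children contributing at each visit.
4. Describe week-9 VABS-3 by week-16 attendance, without a test. On the figures above the non-attending group may be only a few children.

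The cost is a few lines of wording and one extra model, with no new data. The model's assumption is weaker than that of a completers-only test, but selection on unmeasured engagement would remain, and the report should say so. If the final analysis plan already covers items 2 to 4, only the protocol wording needs to be aligned.

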## 5 STUDY POPULATION

The planned sample size is 35 children. There are no limitations related to sex, race or ethnicity.

### 5.1 Inclusion Criteria

In order to be eligible to participate in this study, an individual must meet all of the following criteria:

1. Provision of a parent/guardian signed and dated informed consent form.
2. Stated willingness of parent/guardian to comply with all study procedures and availability for the duration of the study.
3. Child is between 36 months and <132 months of age at baseline.
4. Child has a confirmed DSM-5 diagnosis of both ASD and ADHD, informed by results of assessments including: an ASD diagnostic assessment (Brief Observation of Symptoms of Autism [BOSA], Autism Diagnostic Observation Schedule, 2nd Edition [ADOS-2], or TELE-ASD-PEDS, and if applicable the Autism Diagnostic Interview - Revised [ADI-R]) and an ADHD diagnostic (a standardized ADHD Diagnostic Interview and the MINI psychiatric diagnostic interview).

### 5.2 Exclusion Criteria

An individual who meets any of the following criteria will be excluded from participation in this study:

1. If continuing psychotropic (CNS-active) medications, must not have been changed within 4 weeks prior to baseline.
2. Significant visual, auditory or motor impairments that would preclude participation in ESDM-informed parent coaching or completion of key assessments.
3. Inability of the caregiver participating in ESDM-informed caregiver coaching and responding to questionnaires to fluently speak English.
4. Study clinician judgment that it is not in the best interests of the participant and/or the study for the child to participate (including presence of psychiatric conditions or psychiatric symptoms in addition to ASD and ADHD that in the opinion of the PI or based on senior clinical review, would confound assessments and/or affect participation in the study).

### 5.3 Lifestyle Considerations

None applicable.

### 5.4 Screen Failures

Screen failures are defined as participants who consent to participate in the diagnostic portion and the study but are not subsequently enrolled. Individuals who initially express interest but do not consent to or attend ARC visits will also be considered as part of the number approached for determining rates of enrollment.

### 5.5 Strategies for Recruitment and Retention

The target sample size is 30-35. We anticipate that 20% or less of the sample will be female due to the lower prevalence of both ASD and ADHD among females. We expect that Caucasians will be modestly overrepresented in the sample due to increased historical comfort with clinical trials than minorities. Further, among minorities we anticipate that Hispanic individuals will be most underrepresented in the sample due to requirements that the parent participating in ESDM-informed caregiver coaching be fluent in English. We expect to enroll 1-3 participants per month.

Participants will be recruited from A+ Assessment, A+ Health, A+ Development, community advertisements, medical records, and physician contacts. Recruitment strategies include: developing radio and newspaper ads and brochures, using social media, attending community events, delivering community talks, meeting with various agencies who provide clinical and educational services for children, developing and maintaining active relationships with local autism and ADHD advocacy and support groups, and reaching out to community pediatricians, family practice doctors, child psychiatrists and psychologists, early intervention programs, and schools to make them aware of the treatment needs of children with ASD+ADHD and the availability of A+ Treatment. We will also approach churches and cultural institutions that serve primarily African American, Hispanic and/or Asian populations about giving informational talks and providing informational materials to increase minority recruitment.

**Retention:** A+ Treatment staff including behavioral therapists will maintain regular ongoing contact with all participants and their families to facilitate retention and discuss any concerns that may arise. We anticipate that any concerns will be adequately addressed during the weekly ESDM-informed caregiver coaching visits. If necessary, some parts of the diagnostic and major assessment visits can be split into 2 visits up to one week apart if the family prefers. In addition, the recruitment core may send birthday/holiday cards, distribute newsletters, and e-blasts; provide diagnostic reports that summarize testing results; provide clinical referrals; and give regular updates about Duke ACE Center and DCABD research and activities.

**Incentives for Participation:** We will provide participants with \$50 for completing each visit and its associated assessments, for each coaching session, and for the remote follow-up assessment completion for a maximum of \$550 to help compensate for participation in this protocol. We will also provide incentives for children during assessments and provide each child with a certificate when he/she completes the study. In addition, the opportunity to receive ESDM-informed caregiver coaching as part of the study without extensive waiting and at no cost is anticipated to be an incentive. We will also provide the participant with reports of Vineland and diagnostic assessments if requested.

*Qualitative interviews and surveys with staff, coaches and clinicians:* to prevent any undue influence, clinicians, coaches and staff will be asked by a non-supervisor team member whether they wish to do the qualitative interview/survey, and it will be stressed that they are free to say no, that their decision will have no impact on their employment, performance evaluations, or standing, and that they should only participate if they are completely comfortable doing so. Those who *do* decide to participate in the interview and/or survey will not be provided with compensation beyond what they are paid for that time as part of their study role (this means the time taken to do the interview and/or survey will be done as part of, and will count towards, their regular working hours). To minimize bias when staff, clinicians, and coaches share about their experiences and opinions, and to ensure voluntariness in the consent process, we plan to have a study team member who is not the interviewee's supervisor or mentor conduct the interview and the consent processes.

**Rationale for Selection Criteria:** We have included children between 36 months and < 132 months of age in order to facilitate recruitment. We excluded children below 36 months' chronological age in order to ensure that ADHD can be reliably diagnosed. We are allowing additional comorbid diagnoses or symptoms because studies suggest that a substantial percentage of children with ASD+ADHD will have a third psychiatric diagnosis or other symptoms, and we would not be able to reach our recruitment goals if these children were excluded. Additionally, the study will not exclude participants solely on the basis of a known genetic or neurological condition, as this would unnecessarily prevent otherwise eligible children with ASD and ADHD from participating in and potentially benefiting from this intervention. Furthermore, behavioral intervention is not anticipated to pose an additional risk due to these characteristics; inclusion will also allow for a more representative sample. Participants may be found ineligible if, according to study clinician judgment, it is not in the best interests of the participant and/or the study for the child to participate (including presence of psychiatric conditions or psychiatric symptoms in addition to ASD and ADHD that in the opinion of the PI or based on senior clinical review, would confound assessments and/or affect participation in the study). All children will be administered the Child Behavior Checklist (CBCL), which is a widely-used, well-normed, and empirically validated tool to facilitate diagnosis of other psychiatric problems. If a child has clinically elevated scores, this will be followed up with a semi-structured diagnostic interview by an expert clinician.

**Attrition:** We conservatively estimate that ~15% will not be able to meet the time, technology demands of the study.

